Lodigiani C ¹²	Ward: 326 (84%) ICU: 62 (16%)	75% of ward patients 100% of ICU patients	n=20 (6.4%) n=8 (16.7%)	n=4 (1.3%) n=1 (2.1%)	n=2 (4.2%) n=8 (2.5%)	n=1 (1.9%) n=1 (6.3%)
Zhang ¹⁵	Non COVID-19	281 ICU patients	(9.6%)	n=24	n=1	

Table 3: Thromboembolic complications in patients with COVID-19

The UK already adopts a policy of thromboprophylaxis (after VTE risk assessment) in all hospital inpatients to prevent thrombosis. The risk of thrombosis is compounded in sick patients in HDU/ICU settings by immobility, co-morbidities, (arterial disease, diabetes) body weight, acute inflammatory response and associated therapies e.g. steroids.

UCLH has the largest international cohort of patients with thrombotic thrombocytopenic purpura (TTP) and other thrombotic microangiopathies. Their presentation is acute, associated with anaemia, thrombocytopenia and end organ damage, primarily, the heart, brain and kidney. The respiratory system is not affected in TTP. Other thrombotic microangiopathies (TMA) have variable organ involvement eg HUS does have pulmonary disease. The diagnosis of TMA is primarily clinical, but may be defined by histology. The mainstay of treatment is plasma exchange, using octaplas. The rationale for Octaplas is its safety profile and reduced high molecular weight forms of von Willebrand factor. The role of plasma exchange (PEX) is delivery of high volumes of plasma, replenishing deficient factors e.g. ADAMTS 13, natural anticoagulants/coagulation factors, and complement proteins, leading to normalization of routine laboratory parameters, in particular, FBC, renal function, and LDH. Furthermore PEX has been demonstrated to reduce inflammatory markers, which are extremely high at presentation in TMAs (comparable to levels seen in COVID19) and subsequently ameliorated following PEX. PEX is standard of care for thrombotic microangiopathies, which severe COVID-19 infection appears to mimic.

3.1 Hypothesis:

Patients with COVID-19 have elevated procoagulant factors including VWF and factor VIII secondary to direct endothelial activation. This is associated with an exaggerated pro-inflammatory immune response and microvascular thrombosis; resulting in multi-organ dysfunction and eventually death. PEX will improve coagulopathy, as measured by VWF:ADAMTS 13 ratio and D Dimers, with an associated reduction in inflammation, organ-related microthrombosis, and ventilatory support.

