To compare rates of mechanical ventilation between Plasma Exchange (PEX) and control groups in patients with severe COVID requiring CPAP/ NIV at treatment onset

To compare rates of clinical thrombotic events either venous (deep vein thrombosis DVT or pulmonary embolism PE) or arterial thrombus (cardiac, neurological and peripheral vascular) between Plasma Exchange (PEX) and control groups in patients with severe COVID

To compare reduction in the inflammatory-thrombotic response by monitoring von Willebrand factor VWF antigen/ADAMTS 13 activity ratio between Plasma Exchange (PEX) and control groups in patients with severe COVID

To compare the stability of cardiac function based on echocardiogram/troponin/BNP measurements between Plasma Exchange (PEX) and control groups in patients with severe COVID

To compare incidence of acute kidney injury as defined by KDIGO criteria between Plasma Exchange (PEX) and control groups in patients with severe COVID

To compare mortality at day 28 between the PEX and control groups

6 Trial design

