12.1.2 Secondary outcomes

1. Number of patients requiring mechanical ventilation who required only supplemental O₂/CPAP at study entry. This will be captured throughout the period of the study, by review of the oxygen requirements and ventilatory support required throughout the study (O₂ requirement or PaO₂:FiO₂ (P:F ratio) sequentially)
2. 50% decrease in VWFAg/ADAMTS 13 activity ratio from baseline to end of PEX.
3. Prevent deterioration in myocardial function on ECHO/ cardiac parameters -monitoring of cardiac function through echocardiogram and/ or BNP and Troponin levels throughout study period
4. Clinical thrombotic events documented by imaging either venous DVT/PE, or arterial thrombus (cardiac, neurological and peripheral vascular) throughout the study period
5. Incidence of acute kidney injury as defined by KDIGO criteria throughout study period
6. Mortality at 28 days

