12.2 Sample size and recruitment

12.2.1 Sample size calculation

Mortality of patients on intensive care with COVID-19 has been reported to range from 48% of patients no longer on ITU (ICNARC report on COVID-19 in critical care, 27 Mar 2020) to 86% of patients who required invasive mechanical ventilation (Yang, Lancet Respiratory Medicine, Feb 2020).

We aim to recruit up to 40 patients in total (20 per arm). We will have 80% power to detect a statistically significant difference between the treatment groups at the 5% level assuming that PEX+SOC will reduce inflammation markers in 80% of patients compared to just 20% for SOC if we recruit 20 patients. The power is increased to 99% if 40 patients are recruited. Alternatively, if the effect is lower, e.g. PEX+SOC reduces markers in 65% of patients, then the power will be 85% based on 40 patients.

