12.4.2 Primary outcome analysis

The primary analysis will involve a comparison of the binary outcome ‘50% reduction in at least two inflammation markers’ between the PEX+SOC and SOC trial arms using a chi-squared test. The risk difference (and ratio) will be estimated with a 95% confidence interval. All analyses will be performed on an intention to treat basis.

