12.4.3 Secondary outcome analysis

Secondary outcomes will be summarised and compared using suitable statistical methods. For example, binary outcomes may be compared using chi-squared tests and numerical outcomes may be compared using t-tests. P-values from tests of secondary outcomes may be adjusted to account for multiple testing. Appropriate regression methods will be used to perform adjusted analyses or to account for repeated measures.

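### Secondary outcome 2 cuts the continuous VWF:Ag/ADAMTS13 ratio to a yes/no 50% fall with no baseline-adjusted continuous analysis named; the power cost depends on assumptions and runs from about 2 to about 31 points

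*Combined protocol and SAP*

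**What the plan says.** The hypothesis (synopsis and Section 3.1) states that "PEX will improve coagulopathy, as measured by VWF:ADAMTS 13 ratio and D Dimers". The matching secondary objective in Section 5 is "To compare reduction in the inflammatory-thrombotic response by monitoring von Willebrand factor VWF antigen/ADAMTS 13 activity ratio". It asks for a comparison of reduction and names no threshold.

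Section 12.1.2, item 2, turns this into a responder outcome: "50% decrease in VWFAg/ADAMTS 13 activity ratio from baseline to end of PEX". The documents give no reason for the 50% cut. The primary outcome in Section 12.1.1 gives the control arm a comparable period; item 2 does not say what the end of PEX means for a control patient.

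Section 12.4.3 gives the analysis by example: "binary outcomes may be compared using chi-squared tests and numerical outcomes may be compared using t-tests". It adds: "Appropriate regression methods will be used to perform adjusted analyses or to account for repeated measures". No scale, covariate or time point is named for the ratio.

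Section 9.4.1 and Appendix 3 schedule the samples: before and after each exchange in the PEX arm, and daily in the control arm, through Day 5.

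**The concern.** A responder cut discards most of what the assay measures. A 49% fall counts the same as no fall, and a 51% fall the same as a 90% fall. Baseline enters only as the denominator of the change, so the analysis does not use it to reduce residual variation.

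The trial may stop at 20 patients and will not exceed 40. At that size the choice between a binary and a continuous analysis can decide whether a moderate effect on the ratio is seen. A comparison of proportions also gives no estimate of how far PEX moves the ratio, which is what the objective asks for.

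**Working it through.** **1. Inputs from the documents.** 1:1 allocation; up to 20 per arm, minimum 20 patients in total, so 10 per arm (synopsis, Sections 12.2.1 and 12.3). The 5% level comes from Section 12.2.1 ("statistically significant difference between the treatment groups at the 5% level"); two-sided is assumed. Response rates of 80% v 20% and 65% v 20% also come from Section 12.2.1, but they belong to the primary outcome and are borrowed here.

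**2. Assumed inputs.** A 50% v 20% scenario; a normally distributed change in the log ratio with equal SD in both arms; a correlation r between baseline and change of 0 to -0.5; no missing data. The pilot data (Section 3.2) give only the direction of change.

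**3. Reproducing the plan's own power.** These figures are for the primary outcome, compared "between the PEX+SOC and SOC trial arms using a chi-squared test". With n per arm and p̄ the mean of the two rates:

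power = Φ{ [ |p1 − p2|√n − 1.96√(2p̄(1 − p̄)) ] / √(p1(1 − p1) + p2(1 − p2)) }

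For 80% v 20% with n = 10: (0.6 × 3.162 − 1.96 × 0.707) / 0.566 = 0.904, and Φ(0.904) = 81.7%.

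| Scenario | Stated | Formula | Exact enumeration |
|---|---|---|---|
| 80% v 20%, 10 per arm | 80% | 81.7% | 80.5% |
| 80% v 20%, 20 per arm | 99% | 98.9% | 98.2% |
| 65% v 20%, 20 per arm | 85% | 84.9% | 84.1% |

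The stated powers reproduce with an uncorrected chi-squared test. Exact enumeration of that test is used below.

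**4. Power of the continuous analysis.** If a normal log change gives response rates p1 and p2, the arms differ by d = z(p1) − z(p2) SDs of change: 1.683 for 80% v 20%, 1.227 for 65% v 20%, and 0.842 for 50% v 20%. ANCOVA on baseline divides the residual SD by 1/√(1 − r²), so the noncentrality is d√(n/2)/√(1 − r²), on 2n − 3 degrees of freedom.

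Example, 65% v 20%, n = 20 (critical t 2.026 on 37 df):
- r = 0: 1.227 × 3.162 = 3.88, power 96.5%.
- r = -0.5: (1.227/0.866) × 3.162 = 4.48, power 99.2%.

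Chance baseline imbalance lowers this slightly. The noncentrality is divided by √(1 + t0²/(2n − 2)), with t0 the baseline t statistic on 2n − 2 df, and power is averaged over 200,000 draws. The example becomes 96.1% and 99.0%, so the loss is 96.1 − 84.1 = 12.0 to 99.0 − 84.1 = 14.9 points.

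| Per arm | Rates | Chi-squared | ANCOVA, r = 0 to -0.5 | Loss (points) |
|---|---|---|---|---|
| 20 | 80% v 20% | 98.2% | 99.9–100% | about 2 |
| 20 | 65% v 20% | 84.1% | 96.1–99.0% | 12.0–14.9 |
| 20 | 50% v 20% | 53.1% | 72.6–84.0% | 19.5–30.9 |
| 10 | 80% v 20% | 80.5% | 93.0–97.7% | 12.4–17.2 |
| 10 | 65% v 20% | 52.2% | 71.1–82.6% | 18.9–30.4 |
| 10 | 50% v 20% | 25.4% | 41.0–51.6% | 15.5–26.1 |

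Losses are taken before rounding. Ignoring chance imbalance raises them by at most about 2 points.

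**5. Sensitivity.** A wider simulation varied the log SD (0.4 to 0.8), the baseline-to-follow-up correlation (0.3 to 0.7), the PEX ratio (0.4 to 0.6 of baseline) and the control ratio (0.8 to 1.0 of baseline). The loss ran from 0 to 41 points at 20 per arm (median 25) and from 5 to 68 at 10 per arm (median 31). No single figure can be attached to this trial.

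**The case against.** Four objections carry weight.

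- **The effect may be large.** Section 3 says PEX replenishes ADAMTS13 and that the plasma used has fewer high molecular weight VWF forms, so the treatment acts directly on the ratio. With a strong response both analyses approach full power, and at 80% v 20% with 20 per arm the loss is about 2 points. This stands for full enrolment. At 10 per arm the same rates still lose 12 to 17 points.
- **The plan does not commit to chi-squared alone.** A reader might infer that a yes/no test is the only analysis and that no effect size on the ratio could be reported. Section 12.4.3 does not support that: chi-squared is an example, t-tests are mentioned, and regression for adjustment or repeated measures is promised. But item 2 is written as a binary outcome, and nothing in that section gives the ratio a scale, covariate or time point. In an unblinded trial it is better to settle this beforehand.
- **Its place in the trial.** A reader might also infer that this is the main test of the mechanism, or that the trial's power is undermined. The hypothesis names D-dimer beside the ratio, D-dimer is part of the primary outcome, and the ratio is one of six secondary outcomes with no power claim. The primary power is unaffected.
- **Baseline is not ignored.** It enters through the change from baseline. What is missing is its use as a covariate.

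**Conclusion.** The point holds as a recommended improvement. Item 2 reduces a continuous measurement to a 50% cut although its objective is to compare reduction, and no continuous, baseline-adjusted analysis of the ratio is named.

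Under a normal log change and a baseline-change correlation of 0 to -0.5, the power given up at 20 per arm is about 2 points (80% v 20%), 12 to 15 points (65% v 20%) or 19 to 31 points (50% v 20%). At 10 per arm it is about 12 to 30 points across these rates. Two of the three rate pairs are borrowed from the primary outcome and the third is assumed. A loss quoted without these conditions would go beyond what the documents support.

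**What to change.** Define the main analysis of item 2 as log(VWF:Ag/ADAMTS13 activity) at one Day 5 sample, taken at the same time point in both arms. Compare arms by ANCOVA with the log baseline ratio as covariate, and report the ratio of geometric means with 95% CI. Keep the proportion with a 50% fall as a descriptive summary.

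Two details must be stated:
- Whether the PEX arm contributes its pre- or post-exchange Day 5 sample. Infused plasma supplies ADAMTS13, so the two may differ materially.
- How a death or missing sample before Day 5 is handled. The current responder definition leaves this open as well.

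The cost is mainly wording, since the samples are already scheduled. There are two downsides. The time point moves from the end of PEX to Day 5 for patients who have a second block, so their later values would be described separately. The analysis also assumes approximate normality on the log scale, which should be checked from residuals.

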To compare the stability of cardiac function based on echocardiogram/troponin/BNP measurements cardiac function between Plasma Exchange (PEX) and control groups in patients with severe COVID

To compare incidence of acute kidney injury as defined by KDIGO criteria between Plasma Exchange (PEX) and control groups in patients with severe COVID

To compare mortality at day 28 between the PEX and control groups

Type of trial: A Phase II, Parallel-group, unblinded, randomised controlled trial in COVID 19

Trial design and methods: Patients will receive standard of care (SOC), or SOC and PEX. Single volume PEX capped at 3 litres if <100Kg and 4 litres if >100Kg. PEX will be given once a day for a minimum of 5 days. The course can be repeated at the discretion of the treating clinician, depending on patient's response based on a reassessment on D5-7, where there is clinical and biochemical improvement following initial 5-day block but persistent pro-thrombotic phenotype ie 5 days initial block plus reassess.

Data collection includes routine laboratory parameters, FBC, renal function and liver function; inflammatory markers (D Dimers, LDH, CRP) and pre and post PEX samples to measure von Willebrand factor (VWF) and ADAMTS13 activity levels. The latter samples will be stored for further investigation related to COVID, for example, COVID19 viral analysis, cytokines.

The control patients will have citrate and serum samples taken daily. Following the initial 5 day period. If patients have more than one 5 block of PEX, comparable daily samples will be taken. Thereafter, weekly to day 28.

Trial duration per participant:	From consent to 28 days
Estimated total trial duration:	From when first participant enrolled to last participant follow-up.
Planned trial sites:	Single-site
Total number of participants planned:	Minimum 20, maximum 40

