6.1 Overall design

This a parallel-group randomised controlled trial, which will be unblinded to the investigators and patients .

Patients will be randomised in a 1:1 ratio to either PEX+SOC or SOC. PEX will be delivered in conjunction with standard of care in all patients as dictated by the treating clinicians.

PEX will be given for a minimum of 5 days, but the course can be repeated depending on patient's response, based on a reassessment on D5-7. The 5 day PEX will be repeated at the discretion of the treating clinician in patients showing clinical and biochemical improvement but a persistent pro-thrombotic phenotype following the initial 5-day block .

Patients will be followed up until 28 days post treatment.

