9.4 Subsequent assessments and procedures

9.4.1 Visit schedule and assessments

A schedule of all trial assessments and procedures is set-out in **Appendix 3**.

Day 1- 5

- eligibility check pre PEX if randomised to PEX
- Vitals pre and post PEX (temperature, blood pressure, pulse, respiratory rate and oxygen saturation level) or once daily
- Plasma exchange if randomised to PEX
- assessment of compliance with PEX
- general physical examination
- recording of relevant concomitant medications eg start stop dates of antibiotics, noradrenaline
- Daily routine bloods (FBC, renal, liver function and coagulation screen with fibrinogen)
- Inflammatory markers on D1,D3 &D5 (LDH, CRP, D dimer, ferritin)
- Citrated plasma and serum samples pre and post PEX, or daily for those randomised to SOC to save for VWD screen, ADAMTS13 activity, COVID-19 serology, and multiplex inflammatory markers related to ILs cytokines, interferons, and vascular markers of endothelial injury. Spare samples can be used for COVID-19 related research as authorised by the trial team
- Respiratory parameters: Oxygen requirement, respiratory rate, type of ventilator support-as part of standard of care assessment
- Echocardiogram on D1
- Troponin and BNP on D1
- adverse event collection
- Reactions to Plasma exchange: graded 1-4
- Complications related to central vascath
- Need for antibiotics
- Deterioration requiring ventilation
- Arterial or venous thrombotic event

Reassessment (Day 5-7)

Review of clinical and laboratory parameters by trial team. Consideration of further 5 day block of PEX if clinical and biochemical improvement following initial 5-day block but persistent pro-thrombotic phenotype

*If a patient has a second 5 days of PEX started-follow instructions for day 1-5 above

Follow up Day 6 - 28*

- Vitals (temperature, blood pressure, pulse, respiratory rate)
- general physical examination-weekly
- recording of concomitant medications-related to antibiotics, new cardiac medication, but not all the routine medicines re SOC and not including PRN medications.
- Daily routine bloods (FBC, renal, liver function and coagulation screen with fibrinogen)
- Inflammatory markers, at least 3 x/week (LDH, CRP, D dimer, ferritin)

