12.1 Outcomes

12.1.1 Primary outcomes

The (binary) primary outcome is whether a 50% reduction (from baseline) has been observed in at least two inflammatory markers (based on CRP, LDH and D dimer) throughout the period of PEX or SOC over a comparable time, following initiation of study.

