Appendix 3- Schedule of assessments

	Day 1	Day 2	Day 3	Day 4	Day 5	Day 6	Day 7	Day 14	Day 21	Day 28
FBC	X	X	X	X	X	X	X	X	X	X
Biochemistry	X	X	X	X	X	X	X	X	X	X
Coagulation screen including fibrinogen	X		X		X		X	X	X	X
Inflammatory markers (D Dimer, ferritin, LDH, CRP)	X		X		X		X	X	X	X
Virology testing (Hepatitis A, B,C HIV)	X									
COVID19 Testing	X									

Pregnancy test: serum bHCG	X									
Autoimmune screen: ANA, ENA	X									
Cardiac testing: Troponin/BNP	X				X		X	X	X	X
Procoagulant samples: Pre and post PEX. Daily in non PEX group/following PEX. Including cytokine storm analysis	X	X	X	X	X	X	X	X	X	X
ECG/Echocardia gram	X						X			X
Concomitant mediations eg antibiotics, Noradrenaline	X	X	X	X	X	X	X	X	X	X

Change in respiratory support eg HD oxygen/CPAP/Intubation	X	X	X	X	X	X	X	X	X	X
haemofiltration	X	X	X	X	X	X	X	X	X	X

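### Secondary outcome 2 (VWF:Ag/ADAMTS13 ratio) ends at a time that control patients do not have and that varies among PEX patients, and the plan does not say whether the pre- or post-exchange sample is scored

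*Combined protocol and SAP*

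**What the plan says.** Section 12.1.2, item 2, sets a binary outcome: "50% decrease in VWFAg/ADAMTS 13 activity ratio from baseline to end of PEX". The objective that it serves, in section 5, is "To compare reduction in the inflammatory-thrombotic response by monitoring von Willebrand factor VWF antigen/ADAMTS 13 activity ratio between Plasma Exchange (PEX) and control groups", so both arms need a value.

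The length of PEX is not fixed. Section 6.1 says "PEX will be given for a minimum of 5 days, but the course can be repeated depending on patient's response, based on a reassessment on" Days 5 to 7, and it reserves a further block for patients who have improved but remain pro-thrombotic. Section 9.3 agrees.

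On sampling, section 9.4.1 asks on Days 1-5 for "Citrated plasma and serum samples pre and post PEX, or daily for those randomised to SOC". The synopsis adds that "The control patients will have citrate and serum samples taken daily". The procoagulant row of Appendix 3 reads "Procoagulant samples: Pre and post PEX. Daily in non PEX group/following PEX" and is marked for each of Days 1 to 7, then Days 14, 21 and 28. For Days 6-28, section 9.4.1 asks only for samples at least weekly. No section says which sample closes the interval for item 2.

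The primary outcome does give the control arm a window: "throughout the period of PEX or SOC over a comparable time, following initiation of study". Item 2 has no such phrase.

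Section 3 describes the role of PEX as including "replenishing deficient factors e.g. ADAMTS 13, natural anticoagulants/coagulation factors, and complement proteins".

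**The concern.** There are two separate gaps.

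The first is timing. A between-arm comparison needs an end point that exists in both arms. Item 2's end point exists in one arm only and moves within that arm. A one-block patient would be scored around Day 5. A patient given a second block would be scored several days later, after about twice as many exchanges, and is in that group because of how they responded. The scoring day therefore depends partly on the outcome.

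The second is the sample. Just after an exchange, the patient's plasma is a mixture of their own and donor plasma, so a lower ratio is partly a direct result of the procedure. Before the next exchange, or a day later, much of that may have reversed. If the choice between these samples is left until analysis in an unblinded trial, it can decide the result.

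At stake is what a positive result on item 2 means: that exchange was delivered, or that the patient's inflammatory-thrombotic state changed.

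**Working it through.** **The plan's own figures.** None is given for item 2. The stated power concerns the primary outcome. It reproduces with the pooled normal approximation at two-sided 5%: 81.7% for 80% against 20% at 10 per arm (plan: 80%), 98.9% at 20 per arm (plan: 99%), and 84.9% for 65% against 20% at 20 per arm (plan: 85%). Nothing below changes these.

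**Inputs from the documents.** Section 9.3 gives 40 mL/kg, capped at 3 L below 100 kg, with removal of a comparable volume. Taking 40 mL/kg as one plasma volume, 3 L is 1.0 plasma volumes at 75 kg (3/3.0) and 0.76 at 99 kg (3/3.96). Section 3.2 says that VWF was raised and ADAMTS13 was normal in the pilot, without figures.

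**Assumed inputs.** Entry VWF 200-500%; entry ADAMTS13 80-100%; donor VWF 100%; donor ADAMTS13 70-100%.

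**Model.** One well-mixed compartment with the disease unchanged. The fraction of patient plasma left is f = exp(-volume exchanged / plasma volume). The level after exchange is f × entry + (1 - f) × donor. For one full volume, f = exp(-1) = 0.368.

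**Worked case** (entry VWF 300%, entry ADAMTS13 80%, donor levels 100%):
- VWF: 0.368 × 300 + 0.632 × 100 = 173.6
- ADAMTS13: 0.368 × 80 + 0.632 × 100 = 92.6
- Ratio: from 300/80 = 3.75 to 173.6/92.6 = 1.87, a fall of 50%

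VWF falls to 173.6/300 = 0.58 of entry and ADAMTS13 rises to 92.6/80 = 1.16 of entry, so most of the change comes from removing patient VWF. Donor VWF limits the fall: with none in the product, the ratio would be 110.4/92.6 = 1.19, a fall of 68%.

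**Responders and significance with no lasting effect.** Simulated entry values vary around the figures shown (log-SD 0.3 for VWF and 0.2 for ADAMTS13; plasma volume 3 L, SD 0.4). There is a 20% CV on each measured ratio. The test is the uncorrected chi-squared at 10 per arm, by full enumeration. The fall is for one full-volume exchange from entry levels, measured immediately afterwards.

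| Entry VWF | Entry ADAMTS13 | Donor ADAMTS13 | Fall | Responders | Significant, 10 per arm |
|---|---|---|---|---|---|
| 500% | 80% | 100% | 57% | 68% | 97% |
| 300% | 80% | 100% | 50% | 50% | 80% |
| 300% | 100% | 100% | 42% | 33% | 41% |
| 200% | 80% | 100% | 41% | 31% | 36% |
| 500% | 80% | 70% | 46% | 42% | 63% |
| 300% | 80% | 70% | 37% | 24% | about 20% |
| 200% | 100% | 70% | 16% | 6% | about 0% |

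Without exchange, responders are under 1% with this error, and about 4% if the 20% CV applies to each assay separately.

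**Which sample.** Run the model over five daily full-volume sessions, with donor levels 100% and entry ADAMTS13 80%. Between sessions, let VWF return 50% and ADAMTS13 25% of the way to entry. For entry VWF 300-500%, the fall is 60% to 69% just after session 5 and 36% to 41% a day later. With full return between sessions it is 50% to 57% and then 0%. In these cases the first sample meets the 50% threshold and the second does not.

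**The case against.** Several stronger readings are tempting, and the documents do not support them.

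- **That SOC patients have no usable data, or would be counted as failures.** They are sampled daily in the treatment period, and the synopsis provides for comparable daily samples when there is more than one block. The primary outcome's wording shows what window was probably meant. What is missing is the rule, not the data.
- **That the post-exchange sample is the one scored.** Nothing says so. The end of PEX could equally mean the end of the course, which the Day 6 sample would serve. The defect is that the sample is unspecified.
- **That a positive result would be meaningless.** Section 3.1 states that PEX is expected to improve this ratio, and section 3 presents ADAMTS13 delivery as part of how it works. In a phase II trial the ratio is a legitimate pharmacodynamic outcome. It cannot alone show that the disease response was reduced.
- **That donor VWF produces the fall.** In the model it works against the fall.
- **That the artefact is near certain.** The high figures need high entry VWF and donor ADAMTS13 near 100%. Other values compatible with the pilot description give far less.

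It is also fair to say that a Day 6 sample is not free of exchange. With the partial return used above, 22% to about 30% of PEX patients would still be responders on Day 6 without any change in the disease. Section 12.4.3 says only that chi-squared tests may be used, so the significance figures illustrate one likely analysis.

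What stands is the missing control time, the varying PEX time and the unnamed sample.

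**Conclusion.** The concern holds as a specification gap with a potentially large effect on one secondary outcome. That the end of PEX is undefined for SOC and varies among PEX patients follows from the text alone. The effect of the sample choice is conditional: if the immediate post-exchange sample is scored, exchange alone can, but need not, produce the 50% fall. The range is wide, from a test that almost never rejects to one that almost always does, because entry VWF, donor content, return between sessions and assay error are all assumptions. A reader might infer that the outcome is bound to favour PEX; the documents do not support that. They support the narrower conclusion that the plan leaves open a choice that could determine the result. The defect is confined to item 2 and is worth correcting before analysis.

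**What to change.** In section 12.1.2, item 2, define the outcome as a 50% decrease in the ratio from the Day 1 pre-exchange sample (for SOC, the Day 1 sample) to the Day 6 sample, taken before any exchange that day, in both arms and regardless of any further PEX block. Align section 9.4.1, which is weaker than Appendix 3 after Day 5, with the Day 6 sample that Appendix 3 already schedules. Report immediate post-exchange values descriptively, as a measure of exchange delivery. State that the ratio is read as a pharmacodynamic measure and not, alone, as proof of a reduced inflammatory-thrombotic response.

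The cost is one redefined outcome and one aligned schedule entry, with no sample beyond Appendix 3 and no change to treatment. The PEX response rate on this outcome will probably be lower, and some carry-over may remain on Day 6.

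A smaller change would be to repeat the primary outcome's comparable-time phrase and name the sample. That gives SOC a window but leaves the scoring day dependent on whether a second block was given.
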